	
Safety analysis
 
Adverse event: Treatment-Emergent Adverse Event (TEAEs) should be focused on, i.e. treatment-emergent adverse events. The χ^2 test or Fisher's exact probability method is used to compare the incidence of adverse events in each group and the incidence of adverse events related to the study drug. All adverse events will be coded using the Medical Dictionary for Regulatory Activities (MedDRA) and the number of cases, incidence and frequency of each type of adverse event occurring during the trial will be summarized by SOC/PT. The adverse events occurring in this trial will be tabulated and described.

--	---

Overview of study flow chart of IVIEW 1201

Visit schedule	Visit 1	Visit 2	Visit 3	Visit 4/ EOT	Visit 5/ EOS
Test stage	Screening/Baseline/Day 1	Day 3	Day 6	Day 8	Day 14/ Early withdrawal
Visit window period				(± 1 days)	(± 1 days)
Signing of Informed Consent Form	X				
Inclusion and exclusion criteria	X				
Randomization	X				
Demographic data ¹	X				
History taking ²	X				
Subjective Symptoms Score ³	X	X	X	X	X
Objective Clinical Score ⁴	X	X	X	X	X
Collection of conjunctival sac secretion ⁵	X	X	X	X	X
Vital signs ⁶	X	X	X	X	X
Pregnancy Test ⁷	X				X
Corneal endothelial cell count	X				X
Best-corrected visual acuity	X	X	X	X	X
Corneal fluorescein staining	X	X	X	X	X
Slit-lamp examination	X	X	X	X	X
Intraocular pressure measurement	X	X	X	X	X
Fundus examination	X				X
12-lead ECG examination	X				
Drug allocation ⁹	X				
Study drug administration ¹⁰	X	X	X		
Drug compliance assessment		X	X	X	
Recoding of concomitant medications	X	X	X	X	X
Adverse events ¹¹	X	X	X	X	X
Check of diary card		X	X	X	
Return of drugs				X	X

1.Demographic information: date of birth, gender, ethnicity, height, weight.

2.Medical history collection: including past medical history, surgical history, current medical history (time of onset, cause, etc.), comorbidities, medication history, etc. Any clinically significant examination results other than the research disease found during the screening period should be recorded as medical history.

3.Symptom scoring: Four symptoms (pain, foreign body sensation, photophobia, and tearing) were scored using a 3-point scale (0 = none, 1 = mild, 2 = moderate, 3 = severe). Under the guidance of the researchers, the subjects scored according to the actual situation on the day before the visit and checked in the record form.

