2.2.2 Secondary Endpoints

Clearance rate: The clearance rate of each major pathogenic bacteria at Visit 2, 3, 4 and 5: Stratified analysis shall be conducted according to the type of pathogenic bacteria and the visit time point, and the clearance rate of each kind of bacteria by the investigational drug at different times shall be calculated. Bacterial clearance is defined as positive bacterial culture at baseline and negative bacterial culture at the last visit. Bacterial clearance rate = (number of subjects cleared + number of subjects assumed to be cleared) / total number of subjects enrolled × 100%.

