6.5.3 Biological sample test indicators

Collection of conjunctival sac secretions: Collect a bacterial culture tube and sterile swab from the central laboratory before sampling, and fully expose the bulbar conjunctiva and fornical conjunctiva when sampling. Use a sterile swab moistened with sterile 0.9% sodium chloride solution to gently swab the surface of the conjunctival sac 4 times starting from the inner canthus and rotating from the inside to the outside (pay attention not to missing the inner canthus, and collect the dense secretions), avoid contact with the eyelashes and eyelid margins, and use eyelid speculum and other appliances if necessary. After sampling, put the specimens into a sterile transfer tube, mark them, and send them to the laboratory department of the hospital for bacterial culture. All subjects are required to take secretions from both eyes separately for bacterial culture, with the subject number and eye type indicated.

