7.2 Biological Sample Test Indicators

7.2.1 Bacterial clearance rate

Bacterial clearance is defined as positive bacterial culture at baseline and negative bacterial culture at the last visit.

Bacterial clearance rate = (number of subjects cleared + number of subjects assumed to be cleared) / total number of subjects enrolled x 100%.

For the clearance rate of each major pathogenic bacteria, stratified analysis shall be conducted according to the type of pathogenic bacteria and the visit time point, and the clearance rate of each kind of bacteria by the investigational drug at different times shall be calculated.

The specific judgment criteria are as follows:

Clearance: No pathogenic bacteria of the original infection are cultured in the specimen culture from the original infection site after treatment;

Assumed clearance: Bacteriological results are considered assumed clearance in certain diseases where the disappearance of signs and symptoms makes culturable materials unavailable or the method of obtaining specimens is too invasive for recovered patients;

Not cleared: The pathogenic bacteria of the original infection are still cultured in the specimen culture from the original infection site after treatment;

Assumed not cleared: For patients judged to be clinically ineffective, if the culture has not been done or is unlikely to be done, the pathogenic bacteria can be assumed not cleared;

Partial clearance: At least one of the multiple pathogenic bacteria isolated at the original infection site is cleared at the end of treatment;

Replaced: Those whose bacterial culture results 1 week after treatment show negative results for the original pathogen bacteria and the appearance of new pathogen bacteria, but with no relevant symptoms and signs observed;

Re-infected: Those whose bacterial culture results 1 week after treatment show negative results for the original pathogen bacteria, but with new pathogenic bacteria appearing and signs and symptoms related to re-infection.

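### The bacterial clearance rate counts subjects with no follow-up culture although clearance is defined by a negative culture, and the Visit 5 procedure list omits the swab that would supply it

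*Combined protocol and SAP*

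**What the plan says.** The synopsis (Efficacy Evaluation), Section 2.2.2 and Section 7.2.1 all give the same definition: "Bacterial clearance is defined as positive bacterial culture at baseline and negative bacterial culture at the last visit". Each then gives a formula that is wider than the definition: "Bacterial clearance rate = (number of subjects cleared + number of subjects assumed to be cleared) / total number of subjects enrolled".

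Section 7.2.1 sets out who is assumed cleared: "Bacteriological results are considered assumed clearance in certain diseases where the disappearance of signs and symptoms makes culturable materials unavailable". A second route applies where sampling would be too invasive for a recovered patient. Neither route needs a follow-up culture, and the rule does not repeat the requirement of a positive baseline culture. The counterpart, assumed not cleared, begins: "For patients judged to be clinically ineffective, if the culture has not been done or is unlikely to be done".

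On sampling, Section 6.5.3 says: "All subjects are required to take secretions from both eyes separately for bacterial culture". The method is simple: "Use a sterile swab moistened with sterile 0.9% sodium chloride solution to gently swab the surface of the conjunctival sac 4 times". The flow chart row "Collection of conjunctival sac secretion" is marked at all five visits. The Visit 5 list in Section 6.4 has twelve items, and secretion collection is not one of them.

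**The concern.** A microbiological endpoint is useful because it can disagree with the clinical one. If a missing culture is filled in from the disappearance of signs and symptoms, that independence is lost for exactly those subjects.

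Three features of this trial make it matter:

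- **Natural course.** Section 1.1 describes the disease as self-limiting, with recovery in 10 to 14 days even untreated. By Day 14 many subjects in either arm may be symptom-free, so the rule could reach many subjects and would tend to raise both arms.
- **Open treatment.** Section 3.5 says patients can easily tell the drugs apart; only the assessor is blinded. Four of the seven scored items are self-reported symptoms (6.5.1.1). Culture is less exposed to this, unless it is imputed from symptoms.
- **No other rule.** Section 10.3.3 covers missing data for primary efficacy indicators only. For cultures, the assumed categories are all there is.

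**Working it through.** The plan states no clearance rate, so there is no figure to reproduce. The check has a textual part and an illustrative part.

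**1. Definition against formula.** Take a subject with a positive baseline culture, no signs or symptoms at follow-up and no follow-up culture. By the definition this subject is not a documented clearance, because there is no negative culture. By the formula the subject may be counted through the assumed category. The two sentences give different answers.

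**2. Where cultures can go missing under the plan's own schedule.**

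| Visit | Flow chart | Section 6 list |
|---|---|---|
| 1 | swab | swab (6.1, item 11) |
| 2 and 3 | swab | swab (6.2, item 8) |
| 4 | swab | swab (6.3, item 8) |
| 5 | swab | not listed (6.4) |

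Only Visit 5 is in conflict. It is one of the four visits at which clearance is to be reported, and it is the planned last visit, on which the definition depends.

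**3. The two assumed categories do not mirror each other.** Assumed not cleared is limited to clinically ineffective patients, which Appendix 2 sets at less than 30% reduction in scores. A subject with no culture who has improved by 30% or more but still has signs falls in neither category.

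**4. Size.** All inputs are assumptions and refer to baseline culture-positive subjects:

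- c, share with signs and symptoms gone: 0.7 to 0.9 (example 0.8)
- a, chance of a negative culture if resolved: 0.75 to 0.95 (example 0.85)
- b, chance of a negative culture if not resolved: 0.4
- m, share of resolved subjects with no culture, missing at random among them

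With every culture taken: ca + (1−c)b = 0.8 × 0.85 + 0.2 × 0.4 = 76.0%.

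Under the rule: c[a(1−m) + m] + (1−c)b. At m = 10% this is 0.8 × (0.765 + 0.10) + 0.08 = 77.2%.

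Inflation = c × m × (1−a). At m = 10% the lowest value is 0.7 × 0.1 × 0.05 = 0.35 points and the highest is 0.9 × 0.1 × 0.25 = 2.25 points.

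| m | Rate under the rule (example) | Inflation, example | Inflation, range |
|---|---|---|---|
| 5% | 76.6% | 0.6 points | 0.2 to 1.1 |
| 10% | 77.2% | 1.2 points | 0.4 to 2.3 |
| 50% | 82.0% | 6.0 points | 1.8 to 11.3 |
| 100% | 88.0% | 12.0 points | 3.5 to 22.5 |

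Arm contrast: with a = 0.95 in one arm and 0.75 in the other, and c = 0.8, b and m equal, the difference is 0.8 × 0.20 × (1−m). That is 16.0 points at m = 0, 14.4 at 10%, 8.0 at 50% and 0 at 100%.

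**5. Alternatives on the same example.** Using only subjects with a culture at m = 10%: (0.8 × 0.9 × 0.85 + 0.08) / (0.72 + 0.20) = 0.692/0.92 = 75.2%. Counting missing cultures as not cleared gives 69.2%. At m = 50% the two are 0.42/0.60 = 70.0% and 42.0%, against a true 76.0%. No rule recovers the truth once many resolved subjects go unswabbed, so taking the swab matters more than choosing the imputation.

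**The case against.** A reader might infer that the rule turns clearance into clinical cure under another name. The documents do not support that:

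- The swab is listed in both places for Visits 2, 3 and 4.
- A culture that still grows the original organism is classed as not cleared in 7.2.1, whatever the symptoms.
- The trigger is disappearance of signs and symptoms, whereas clinical cure (7.1) is two sign scores of 0.
- In the example above, agreement between clearance and clinical resolution is 80.0% with full culture, 81.2% at m = 10% and 92.0% at m = 100%. It reaches 100% only if nobody is cultured and all unresolved subjects are assumed not cleared.

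It can also be said that assumed clearance requires material to be unavailable, not merely a swab not taken; only the counterpart rule mentions cultures not done. That is a fair reading. The wording is loose enough, though, that symptom-free subjects at a site following 6.4 could be classed either way.

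Section 7.2.2 already plans a negative conversion rate among baseline-positive patients, based on cultures alone. This helps, but it is not the named secondary endpoint and has no stated visit. The pathogen table in 7.2.2 has no assumed column, so it does not show where such subjects would go.

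Finally, the size is easily overstated. Suppose 40 of 60 subjects in an arm are culture-positive at baseline; afterwards 24 are negative, 6 positive and 10 unswabbed, 9 of these symptom-free. Then (24 + 9)/40 = 82.5% against 24/40 = 60.0% looks like a 22.5-point effect. Among those cultured, however, the rate is 24/30 = 80.0%, so the rule adds 2.5 points and the other 20 come from counting missing cultures as failures. With the written denominator of all enrolled, the formula gives 33/60 = 55.0%.

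**Conclusion.** The inconsistency is real and rests on the text alone: the definition needs a negative culture and the formula does not. The stated rationale has little place in a trial that swabs both eyes of every subject. The omission in 6.4 makes Visit 5 the point of exposure; there, clearance could lean on clinical outcome at sites that follow the list rather than the flow chart.

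How much this matters depends on how many cultures are missing. At 5 to 10% of resolved subjects uncultured, the inflation is about 0.2 to 2.3 points; at 50% it is 1.8 to 11.3 points, and half of any arm difference among resolved subjects is lost. These figures assume the ranges for c and a above, b = 0.4, and missingness at random among resolved subjects. They are per baseline culture-positive subject; on the written all-enrolled denominator they shrink in proportion to the baseline-positive share, if only those subjects can count. The point should be corrected, but it does not undermine the endpoint at Visits 2 to 4.

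**What to change.** 1. Reconcile the Section 6.4 list with the flow chart so that the Visit 5 culture is available.
2. In the synopsis, 2.2.2 and 7.2.1 together, base the main clearance rate on documented cultures in baseline culture-positive subjects, at the visit being reported.
3. Report assumed cleared as a separate row by arm and visit, next to the number of missing cultures, and say how a partly improved subject without a culture is classed.
4. Prespecify two sensitivity analyses: missing cultures in symptom-free subjects as assumed cleared, and all missing cultures as not cleared. The second is a lower bound. It should not be the only rule, since it penalises recovered subjects who were not swabbed.

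The cost is wording in four places and a little more analysis. No procedure is added, because the flow chart already has the swab. The reported clearance rate may be lower than under the present formula.

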7.2.2 Evaluation of specific etiological efficacy

(1) Bacterial culture positivity rate = the number of positive bacterial culture as a percentage of the total number of cases in the study.

(2) Bacterial species clearance rate = the total number of bacterial species cleared as a percentage of the total number of pathogenic species isolated at the end of treatment.

(3) Negative conversion rate of bacterial culture = The percentage of patients whose bacterial culture turns negative after treatment among those with positive bacterial culture before treatment.

(4) Stratified evaluation of pathogens

① Analysis of 120 patients at the end of all studies

Pathogen/Number of patients	Cleared	Not cleared	Replaced	Re-infected
Staphylococcus aureus				
Streptococcus pneumoniae				
Haemophilus influenza				
Corynebacterium				
Streptococcus hemolyticus				

② Observation of different pathogens for different duration of administration

Duration of administration / Number of patients	Staphylococcus aureus	Streptococcus pneumoniae	Haemophilus influenza	Corynebacterium	Streptococcus hemolyticus
Baseline					
Visit 2					
Visit 3					
Visit 4					
Visit 5					

8. Compliance

Compliance will be determined by subject self-report as recorded in subject diaries. Missing diary data may be collected by subject questioning. There will also be drug dispensing and return logs to be completed by the investigative site.

% = actual number of medication times / theoretical number of medication times × 100%.

A calculated result less than 80% or greater than 120% was considered to be poor compliance

9. Assessment of Safety

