3.4 Number of Subjects

This study preliminarily observed the efficacy and safety of IVIEW-1201 (1.0% povidone-iodine ophthalmic gel sterile solution) in the treatment of acute bacterial conjunctivitis, and no statistical analysis on the sample size is performed. Based on the safety evaluation requirements, 60 cases were set in the experimental group and 60 cases in the control group.

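### Section 7.2.2(2), as printed, divides cleared species by those isolated at the end of treatment, so the species clearance rate is not a proportion and can exceed 100%.

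*Combined protocol and SAP*

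**What the plan says.** Section 7.2.2 lists measures of etiological efficacy. Item (2) counts species "cleared as a percentage of the total number of pathogenic species isolated at the end of treatment".

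Section 7.2.1 supplies the meaning of clearance: "No pathogenic bacteria of the original infection are cultured in the specimen culture from the original infection site after treatment". It also provides for organisms that were absent at the start. The replaced category covers subjects whose cultures a week after treatment "show negative results for the original pathogen bacteria and the appearance of new pathogen bacteria" without related symptoms or signs. The re-infected category is similar, but with symptoms and signs.

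Item (3) of section 7.2.2, the negative conversion rate, takes its percentage "among those with positive bacterial culture before treatment", that is, on a pre-treatment base.

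The document gives no other definition of the species rate and does not say whether a species is counted once per arm or once per subject.

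**The concern.** A clearance rate should say what share of the organisms present at the start has gone. That needs a denominator fixed at baseline, with the numerator a subset of it. Item (2) as printed takes its denominator from the end of treatment, when a cleared organism is by definition no longer found. The denominator then shrinks as clearance improves, and it grows when an organism appears that was never there to be cleared.

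Item (2) is the only rate in section 7.2 that counts organisms instead of subjects. A programmer who follows it literally would produce percentages that cannot be read as such. A programmer who quietly repairs it would choose the denominator at the analysis stage, outside the plan.

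**Working it through.** The plan states no value for this rate, so there is no figure to reproduce. The check is on the definition.

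**Inputs**
- Numerator: species cleared, C (7.2.2(2)).
- Printed denominator: species isolated at the end of treatment, E (7.2.2(2)).
- Cleared means that the original pathogen is no longer cultured after treatment (7.2.1).
- New pathogens may be isolated after treatment (7.2.1); call their number at the end of treatment K.
- Baseline pathogens, B: not given. B = 50 is assumed for illustration. With K = 0 the result depends only on C/B, not on B itself.
- Counting unit: not given. Each pathogen is counted once within each subject.

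**Formulas**
- Organisms isolated at the end of treatment: E = B − C + K (persisting plus new).
- Rate as printed: 100 × C/(B − C + K).
- Rate on a baseline denominator: 100 × C/B.
- The printed rate exceeds 100% when C > B − C + K, that is, when C > (B + K)/2. With K = 0 this means more than half cleared.
- With K = 0 and c = C/B, the printed rate is the odds c/(1 − c) written as a percentage.

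**Results for B = 50**

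| Cleared, C | Baseline denominator | As printed, K = 0 | As printed, K = 5 |
|---|---|---|---|
| 15 | 30% | 15/35 = 42.9% | 15/40 = 37.5% |
| 25 | 50% | 25/25 = 100% | 25/30 = 83.3% |
| 30 | 60% | 30/20 = 150% | 30/25 = 120% |
| 40 | 80% | 40/10 = 400% | 40/15 = 266.7% |
| 45 | 90% | 45/5 = 900% | 45/10 = 450% |
| 50 | 100% | 50/0, undefined | 50/5 = 1000% |

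The row for 45 cleared shows the second effect. Eradication of the original pathogens is the same in both printed columns, yet five new organisms halve the figure from 900% to 450%. The last row shows that the rate is undefined only when no new pathogen is isolated; otherwise it has a value, but not one that can be read as a percentage.

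**The case against.** The strongest defence is that the closing time phrase dates the clearance assessment and not the isolation. Section 7.2.1 uses it that way for partial clearance: "At least one of the multiple pathogenic bacteria isolated at the original infection site is cleared at the end of treatment". On that reading the denominator is all pathogens isolated, and the fault is one of word order. This is plausible, and it rules out claiming that the authors intended an end-of-treatment denominator. It does not remove the need for a correction. As printed, the phrase follows the word for isolation, and even the kinder reading leaves the denominator without a time point, although cultures are scheduled at every visit from Visit 1 to Visit 5 in the study flow chart.

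A second objection concerns the counting unit. If distinct species are pooled across an arm, a species cleared in one subject may still grow in another, so numerator and denominator can overlap. This stands. The arithmetic above holds for pathogens counted within subjects, and the missing unit is a further gap to close.

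Third, the effect on the trial is small. The rate is not among the primary, secondary or exploratory endpoints in section 2.2. Section 10.3.4 names no comparison of it between arms. Item (3) and the pathogen tables in section 7.2.2(4) would let a reader build a baseline-based figure for the five listed pathogens, and a value such as 900% would be noticed at once. This also stands.

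Two stronger readings are tempting. A reader might infer that the formula would distort the comparison of treatments; with no such comparison named and no isolate counts given, the documents do not support that. A reader might also infer that every new organism falls under the replaced or re-infected label. Section 7.2.1 defines both more narrowly: the original pathogen must be negative and the culture is taken a week after treatment, so a new organism beside a persisting original one fits neither.

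**Conclusion.** The definition is wrong as printed and should be corrected. Counting each pathogen within each subject, it gives cleared/(persisting + new) and not a proportion of the organisms at risk of clearance. With no new organisms it exceeds 100% once more than half of the baseline pathogens are cleared. It is undefined when all are cleared and no new pathogen is isolated; a reader might infer that complete clearance always leaves it without a value, but that holds only under the second condition.

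The sizes shown rest on an assumed 50 baseline pathogens and an assumed 0 or 5 new ones. The direction of the error does not depend on those choices; it depends on the counting unit and on taking the sentence as printed. Since this is a supporting measure outside the listed endpoints, the matter is a correction to make before analysis and does not threaten the primary result.

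**What to change.** Replace section 7.2.2(2) with a definition of this kind:

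- **Numerator:** baseline pathogens no longer cultured at Visit 4/EOT.
- **Denominator:** pathogens isolated at baseline.
- **Unit:** each pathogen counted once per subject, from the target eye (the term in section 10.3.4), which should be tied to the original infection site (the term in section 7.2.1).
- **Rate:** numerator/denominator × 100%.

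Keep organisms first isolated after baseline out of both counts and report them separately. Use the replaced and re-infected labels only where the section 7.2.1 definitions are met.

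With this definition the rate stays between 0% and 100%: in the illustration, 40, 45 and 50 of 50 cleared give 80%, 90% and 100%, whatever the number of new organisms.

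The cost is one sentence in the protocol, repeated in any separate analysis plan that carries the formula. The cultures needed are already scheduled at Visit 1 (section 6.1) and Visit 4 (section 6.3), and no visit, procedure or treatment changes.
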